5.2.2 Assessment of effectiveness

HbA_{1c}:

HbA_{1c} should be collected within 1 month prior to baseline and after 12 weeks and 24 weeks of treatment.

Fasting plasma glucose (FPG):

FPG should be collected within 1 month prior to baseline and after 12 weeks and 24 weeks of treatment.

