6.2.2.1 Visit 1 – Baseline Visit

Upon patient enrollment, the following will be recorded on the patient's eCRF.

- Visit date
- Diagnosis: date of the diagnosis of T2DM, family history
- Inclusion / exclusion criteria
- Demographic data: year of birth (age), gender, pregnancy, previous allergy, height, weight, waist circumference, smoking status
- Diabetes mellitus related complication
- Other medical history: history of concomitant disease within 6 months
- Renal Function: record Serum creatinine, eGFR, urin ACR if blood test result is available (collected within the latest 6-month period)
- Effectiveness endpoints : HbA_{1c}, FPG (Lab data should be collected within 1 month prior to baseline)
- Concomitant anti-hyperglycemic agent: record any anti-hyperglycemic agents have been taken prior to the baseline visit
- Concomitant medications: record all medications have been taken at least once since one month prior to the baseline visit
- Dose of Trajenta given

At Visit 1, the patient will be requested to contact the treating physician in the event of any adverse events noted after initiating Trajenta treatment.

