6.1 Demographics and Baseline Characteristics

Data for the demographics and baseline characteristics in safety analysis set is demonstrated by descriptive statistics. In the descriptive statistics, number of subjects, mean, standard deviation, median, minimum and maximum will be calculated for continuous variables, and frequency and percentage will be presented for categorical variables.

The following demographics and baseline characteristics will be reported.

< Demographic information >

- Age, Gender, Pregnancy, Allergy, Height, Weight, Waist circumference, Smoking status, Diabetes mellitus complications and their classification, Other medical history and its classification, duration of T2DM, Family history, Pediatric group (Under 19 years), Geriatric group (65 years or older), Kidney disorder, Liver disorder, Subjects whose drug administration period of long-term (24 weeks or more)

< Medication information >

- Concomitant medication and its classification, Trajenta administration status (Total administration period of Trajenta, Total administration dose of Trajenta), Reason of prematurely study withdrawal, Other anti-diabetic agent and its classification

	CONFIDENTIAL :	Last Update Date
	THIS DOCUMENT AND INFORMATION CONTAINED HEREIN IS PROPRIETARY TO COMPANY AND IS NOT TO BE DISCLOSED WITHOUT THE WRITTEN PERMISSION OF COMPANY.	21-AUG-2017
STATISTICAL ANALYSIS PLAN(V3.0)		

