6.2 Effectiveness Analyses

Effectiveness analysis shall be conducted for subjects of the effectiveness analysis set.

The change from baseline to last visit of HbA1c will be calculated for each subject. The difference of HbA1c between baseline and last visit shall be described by mean, and shall be analyzed with paired t-test.

According to the following baseline characteristics, the change from baseline to last visit of HbA1c will be analyzed with t-test or ANOVA (Analysis of Variance).

- Age, Gender, Pregnancy, Allergy, Diabetes mellitus complications and their classification, Other medical history and its classification, duration of T2DM, Family history, Pediatric group (Under 19 years), Geriatric group (65 years or older), Kidney disorder, Liver disorder, Subjects whose drug administration period of long-term (24 weeks or more), Concomitant medication and its classification, Total administration period of Trajenta, Reason of prematurely study withdrawal, Other anti-diabetic agent and its classification

If necessary, analysis for the impact of the change from baseline to last visit of HbA1c may be carried out using multiple regression analysis. In general, the variables corresponding to the baseline characteristics listed in section 6.1 are used as an independent variable. However, as considering the structure and characteristics of the collected data, the variables used for the actual analysis can be added or subtracted.

The frequency and percentage of the final effectiveness assessment will be summarized.

The final effectiveness assessment of “Improved” will be classified as “Effective”. The final effectiveness assessment of “No changed” and “Worsened” will be classified as “Ineffective”. The effectiveness rate and its 95% confidence intervals will be estimated with exact method.

The effectiveness rate will be analyzed according to the baseline characteristics listed in section 6.1. Chi-square test or Fisher’s exact test will be used for comparing between subcategories of each baseline characteristic and will be estimated with its 95% confidence interval.

According to the following subgroup, the frequency and percentage of subjects whose HbA1c of <

	CONFIDENTIAL :	Last Update Date
	THIS DOCUMENT AND INFORMATION CONTAINED HEREIN IS PROPRIETARY TO COMPANY AND IS NOT TO BE DISCLOSED WITHOUT THE WRITTEN PERMISSION OF COMPANY.	21-AUG-2017
STATISTICAL ANALYSIS PLAN(V3.0)		

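### Baseline HbA1c and FPG are collected but are missing from the SAP's baseline list, subgroup list and default regression covariates, so unadjusted subgroup differences in HbA1c change may partly reflect different starting levels

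*SAP*

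**What the plan says.** **Collection.** Protocol 5.2.2 says that HbA1c and FPG "should be collected within 1 month prior to baseline and after 12 weeks and 24 weeks of treatment". Protocol 6.2.2.1 repeats this for Visit 1: "Lab data should be collected within 1 month prior to baseline".

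**Baseline list.** SAP 6.1 introduces its list with "The following demographics and baseline characteristics will be reported". The demographic part has 17 entries, from age to long-term administration, and includes "Family history, Pediatric group (Under 19 years), Geriatric group (65 years or older), Kidney disorder, Liver disorder, Subjects whose drug administration period of long-term". The medication part ends with "Reason of prematurely study withdrawal, Other anti-diabetic agent and its classification". Neither part contains HbA1c or FPG, and the matching table list in SAP 7.2 does not either.

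**Subgroup comparisons.** For a list of characteristics that again omits both values, SAP 6.2 says that "the change from baseline to last visit of HbA1c will be analyzed with t-test or ANOVA (Analysis of Variance". No covariate is named.

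**Regression.** SAP 6.2 makes multiple regression of HbA1c change conditional on need. By default, "the variables corresponding to the baseline characteristics listed in section 6.1 are used as an independent variable". Variables may be added or removed in the light of the collected data, but none is named.

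**Status of the results.** SAP 8 sets two-sided tests at 0.05. Protocol 7.1 describes all analyses as descriptive, with exploratory p-values and no confirmatory hypotheses. Effectiveness is the secondary objective (Protocol 2.2.2, SAP 1.2).

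**The concern.** Change is follow-up minus baseline, so it is arithmetically tied to baseline. A patient who starts at 6.6% has less room to fall than one who starts at 10%. The entry criteria set no HbA1c range. SAP 3.1 allows monotherapy and several combinations, including insulin, so starting HbA1c may well differ between the groups that SAP 6.2 compares, for example by diabetes duration, kidney disorder or other anti-diabetic agents.

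A significant difference in HbA1c change between such groups could be read as a difference in response to Trajenta when part of it comes from different starting levels. The response rates have the same problem. A patient already below 6.5% at entry can count as at target at the last visit without any fall, and the 0.5-point response is harder to reach from a low start. Protocol 3.2 warns that only major confounders can be captured. Baseline HbA1c is captured, but the analysis lists do not use it.

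**Working it through.** **Step 1: the text.** The documents give no figure to reproduce on this point. The 3,000 patients in Protocol 7.6 are a regulatory number, with no SD, effect size or power behind it. Reading SAP 6.1, 6.2, 7.2 and 7.3 together confirms three omissions: from the reported baseline characteristics, from the subgroup list, and (by reference to 6.1) from the default regression covariates.

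**Step 2: size of the baseline-related difference.** Assumptions, none from the documents: slope of change on baseline -0.3, -0.5 or -0.7; baseline gap between two subgroups 0.1 or 0.3 HbA1c points.

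Difference in mean change = slope × gap.
- Smallest: 0.3 × 0.1 = 0.03 points.
- Largest: 0.7 × 0.3 = 0.21 points.

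**Step 3: chance that the planned unadjusted test is significant.** Further assumptions: SD of change 1.0 or 1.3; all 3,000 patients analysed, split 1,500/1,500 or 2,400/600; no subgroup difference other than the one in Step 2. A smaller effectiveness set would lower these figures.

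SE = SD × √(1/n₁ + 1/n₂), for example 1.0 × √(1/2400 + 1/600) = 0.0456. Chance of p < 0.05 = Φ(d/SE − 1.96) + Φ(−d/SE − 1.96), where d is the size of the difference.

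| Gap | Slope | d | 1,500/1,500, SD 1.0 | 1,500/1,500, SD 1.3 | 2,400/600, SD 1.0 | 2,400/600, SD 1.3 |
|---|---|---|---|---|---|---|
| 0.1 | -0.3 | 0.03 | 13.0% | 9.7% | 10.1% | 8.0% |
| 0.1 | -0.5 | 0.05 | 27.8% | 18.4% | 19.5% | 13.4% |
| 0.1 | -0.7 | 0.07 | 48.3% | 31.4% | 33.5% | 21.8% |
| 0.3 | -0.3 | 0.09 | 69.3% | 47.5% | 50.5% | 32.9% |
| 0.3 | -0.5 | 0.15 | 98.4% | 88.5% | 90.8% | 71.5% |
| 0.3 | -0.7 | 0.21 | about 100% | 99.3% | 99.6% | 94.3% |

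The range is 8% to 48% for a 0.1-point gap and 33% to nearly 100% for a 0.3-point gap.

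**Step 4: effect of adjustment if response truly depends on measured baseline.** Simulation, 1,000 runs per setting, 1,500 v 1,500, assumed baseline SD 1.2 and residual SD 0.8. With a 0.3-point gap the unadjusted t-test rejected in 81.8% to 99.9% of runs. With baseline HbA1c in the model, rejection was 3.8% to 5.7%.

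**Step 5: effect of adjustment if the slope is only regression to the mean.** Let both groups have the same true change, and let baseline and follow-up be measured with reliability ρ. The slope of change on baseline is then −(1 − ρ). The unadjusted difference is 0, and the baseline-adjusted difference is (1 − ρ) × gap. With ρ = 0.7 (assumed) the slope is -0.3, and a 0.5-point gap gives an adjusted difference of 0.3 × 0.5 = 0.15 points. In simulation (2,000 v 500, baseline SD 1.2, so SD of change √(2 × 0.3 × 1.2²) = 0.93), the unadjusted test rejected in about 5% of runs and the adjusted one in about 93%.

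Steps 4 and 5 are the two extremes. The documents do not show where this study lies between them.

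**The case against.** **Adjustment is not automatically better.** Step 5 shows that in pre-existing groups the change-score comparison can be the unbiased one, and that adjustment for baseline can then create a difference. This stands. It rules out replacing the planned tests outright, and it means that the Step 2 difference cannot simply be called spurious.

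**The inputs are assumed.** Slope, gap, SD and split are all illustrative, and with a small gap the effect on the tests is modest. This also stands, so a range is given.

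**The SAP lets variables be added.** It does, but it names none, the choice follows a look at the data, and the regression is run only if judged necessary. The t-test or ANOVA is not conditional. The clause permits adjustment but does not plan it.

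**Baseline HbA1c may be reported anyway.** A reader might infer that starting values will be withheld. The documents do not support that. HbA1c and FPG are endpoints, each change is measured from baseline, and SAP 8 gives summary statistics for continuous variables. Reporting is not excluded, but no listed table requires it.

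**Prior DPP-4 inhibitor use.** A reader might take this as a planned unadjusted between-group test. SAP 6.2 sets users and non-users out as separate sets, and SAP 7.3 lists mean, SD and p-value for HbA1c change by that status without saying that the two are compared. The point therefore does not rest on this example.

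**The analyses are descriptive.** True, and it limits the weight. Even so, p-values at 0.05 are planned for each subgroup factor, and readers will interpret them.

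**Conclusion.** The omission is confirmed, and its consequence is a possibility of unknown size. Subgroup differences in HbA1c change, as planned, may partly reflect different starting HbA1c. Under the Step 2 assumptions the baseline-related part is about 0.03 to 0.21 points, and some of it may be regression to the mean.

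A reader might go further and infer that significant subgroup results will be false, or that ANCOVA must replace the t-test and ANOVA. Neither follows. The first needs a slope and a gap that the documents do not give. The second fails if the slope is largely regression to the mean.

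The overall paired t-test of HbA1c change and all safety results are unaffected. Because effectiveness is secondary and descriptive, this is an inexpensive improvement to make before analysis and does not threaten the study's main conclusions.

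**What to change.** 1. Add baseline HbA1c and FPG to the tables in SAP 6.1 and 7.2.
2. Add baseline HbA1c band, with cut points fixed before analysis, to the SAP 6.2 subgroup list. Tabulate HbA1c change and the rate of falls of at least 0.5 points by band.
3. Name baseline HbA1c as a fixed covariate in the regression of HbA1c change. This loses no patients, because a change score already needs a baseline value.
4. Keep the planned t-test and ANOVA, and show baseline-adjusted (ANCOVA) estimates beside them. Note that neither removes all confounding in non-randomised subgroups.
5. State that baseline HbA1c and FPG do not enter the adverse-event logistic regression in SAP 6.3.1 automatically. That model also takes its variables from 6.1, laboratory tests are not required (Protocol 7.4) and nothing is imputed (SAP 6.4). Automatic entry would therefore drop patients with missing values from a model that serves the primary objective.

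The cost is SAP wording, a few table rows and some extra analysis. No new data are needed.

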6.3 Safety Analyses

In the safety analysis set, the number of subjects with AEs and the number of AEs will be calculated. Also, the incidence proportion of AEs will be estimated with its 95% confidence interval.

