7.1 STATISTICAL DESIGN - MODEL

In this non-interventional study, all statistical analyses will be descriptive. The degree of statistical significance (p-values) and precision (confidence intervals) for the statistical methods used for explorative purposes will be shown. No confirmatory hypotheses are pre-specified.

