7.6 DETERMINATION OF SAMPLE SIZE

Sample size of 3,000 patients is based on the requirement of the local regulatory authority (Korean FDA). As per regulation, long-term surveillance is necessary for the indication. Since T2DM is chronic disease, it might be restrictive to collect safety and effectiveness data in short-term (12±2weeks) period, all patients will be enrolled for longer-term (24±2weeks) surveillance.

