2.2 Number of Subjects

A total of 3,000 patients will be enrolled at approximately 80 sites by as many as 100 or more NIS physicians. To minimize the selection bias at the site level, the goal is to have participating centers reflect a balance between general hospitals and clinics for surveillance. The treating physicians will mainly be internists. To minimize the selection bias, consecutive patients from each site who meet inclusion criteria will be enrolled in this study.

	CONFIDENTIAL :	Last Update Date
	THIS DOCUMENT AND INFORMATION CONTAINED HEREIN IS PROPRIETARY TO COMPANY AND IS NOT TO BE DISCLOSED WITHOUT THE WRITTEN PERMISSION OF COMPANY.	21-AUG-2017
STATISTICAL ANALYSIS PLAN(V3.0)		

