6.3.1 Adverse Events by Demographics and Baseline Characteristics

For the AE(s) by demographics and baseline characteristics in the safety analysis set:

- The number of subjects to whom AE occurred and the number of AEs will be calculated.
- The incidence proportion of AEs and its 95% confidence interval will be estimated. Chi-square test or Fisher's exact test will be used for comparing between subcategories of each demographics and baseline characteristics.
- If necessary, analysis for the impact of the safety may be carried out using logistic multiple regression analysis. In general, the variables corresponding to the baseline characteristics listed in section 6.1 are used as an independent variable. However, as considering the structure and characteristics of the collected data, the variables used for the actual analysis can be added or subtracted.

	CONFIDENTIAL :	Last Update Date
	THIS DOCUMENT AND INFORMATION CONTAINED HEREIN IS PROPRIETARY TO COMPANY AND IS NOT TO BE DISCLOSED WITHOUT THE WRITTEN PERMISSION OF COMPANY.	21-AUG-2017
STATISTICAL ANALYSIS PLAN(V3.0)		

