7.3 Effectiveness Analyses

- Mean, SD and p-value on the change from baseline to last visit of HbA1c
- Mean, SD and p-value on the change from baseline to last visit of HbA1c by baseline characteristics

	CONFIDENTIAL :	Last Update Date
	THIS DOCUMENT AND INFORMATION CONTAINED HEREIN IS PROPRIETARY TO COMPANY AND IS NOT TO BE DISCLOSED WITHOUT THE WRITTEN PERMISSION OF COMPANY.	21-AUG-2017
STATISTICAL ANALYSIS PLAN(V3.0)		

- Frequency and percentage on final effectiveness assessment
- Effectiveness rate and 95% confidence interval on final effectiveness assessment
- Frequency, effectiveness rate, 95% confidence interval and p-value on final effectiveness assessment by baseline characteristics
- Frequency and percentage on subjects whose HbA1c of < 6.5% at last visit
- Frequency and percentage on subjects whose HbA1c lowering is at least 0.5% at last visit
- Mean, SD and p-value on the change from baseline to last visit of FPG
- According to whether or not administered Tragenta for more than 24 weeks and whether or not administered DPP-4 inhibitor before administration of Trajenta, Mean, SD and p-value on the change from baseline to last visit of HbA1c.
- According to whether or not administered Tragenta for more than 24 weeks and whether or not administered DPP-4 inhibitor before administration of Trajenta, frequency and percentage on subjects whose HbA1c of < 6.5% at last visit.
- According to whether or not administered Tragenta for more than 24 weeks and whether or not administered DPP-4 inhibitor before administration of Trajenta, frequency and percentage on subjects whose HbA1c lowering is at least 0.5% at last visit.
- According to whether or not administered Tragenta for more than 24 weeks and whether or not administered DPP-4 inhibitor before administration of Trajenta, Mean, SD and p-value on the change from baseline to last visit of FPG.
- Multiple regression analysis on the change of HbA1c

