7.4 Safety Analyses

- According to the baseline characteristics, incidence proportion and the number of AEs (frequency and percentage)
- The number of AEs for serious adverse event, intensity, outcome of the event, action taken, causality, therapy of the event (frequency and percentage)
- The number of AEs for serious adverse event, intensity, outcome of the event, action taken, causality, therapy of the event by preferred terms (frequency and percentage)
- For safety analysis set, according to whether or not administered Tragenta for more than 24 weeks and whether or not administered DPP-4 inhibitor before administration of Trajenta, the number of AE/ADR, Serious AE/Serious ADR, unexpected AE/ADR, unexpected Serious AE/unexpected Serious ADR by preferred terms (frequency, percentage, incidence proportion and its 95% confidence interval)
- Preferred terms of Serious AE/Serious ADR, unexpected AE/ADR according to the proportion of AE

	CONFIDENTIAL :	Last Update Date
	THIS DOCUMENT AND INFORMATION CONTAINED HEREIN IS PROPRIETARY TO COMPANY AND IS NOT TO BE DISCLOSED WITHOUT THE WRITTEN PERMISSION OF COMPANY.	21-AUG-2017
STATISTICAL ANALYSIS PLAN(V3.0)		

- For subjects excluded from the safety analysis set[†], the number of AE/ADR, Serious AE/Serious ADR, unexpected AE/ADR, unexpected Serious AE/unexpected Serious ADR according to the preferred terms (frequency, percentage, incidence proportion and its 95% confidence interval)
- Multiple logistic regression analysis on the incidence proportion of AEs
 - †Subject excluded from safety analysis set: ‘Subjects who didn’t receive Trajenta’ and ‘Follow-up failure’ of patients excluded from safety analysis sets will be excluded (Reflecting the Ministry of Food and Drug Safety (MFDS) guideline).

8. Note

- Each statistical analysis will be carried out with SAS Software version 9.4 or more recent version.
- In the descriptive statistics, mean, SD, median, minimum and maximum will be calculated for continuous variables, and frequency and percentage for categorical variables.
- Data including sign of inequality such as “≥20”, “>20” will be excluded from analysis.
- All test statistics will be the results of two-sided tests with the statistical significant level of 0.05.
- The followings shall be included only in re-examination report:
 - Estimation of 95% confidence interval for incidence proportion of AEs by baseline characteristics

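### The SAP plans no confidence interval for HbA1c change, FPG change or the two HbA1c responder rates, although the protocol promises intervals, and no analysis allows for clustering of patients within about 80 sites

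*SAP*

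**What the plan says.** **Intervals.** Protocol 7.1 says that, alongside p-values, "precision (confidence intervals) for the statistical methods used for explorative purposes will be shown". Protocol 5.2.1 makes change in HbA1c the main effectiveness endpoint, with two HbA1c responder rates and FPG change as the others. SAP 6.2 states that the HbA1c difference "shall be described by mean, and shall be analyzed with paired t-test", and the output listed in SAP 7.3 is "Mean, SD and p-value on the change from baseline to last visit of HbA1c". FPG change has the same output. The responder rates (HbA1c below 6.5%, and a fall of at least 0.5%) have frequency and percentage only. SAP 6.2 does plan an exact 95% interval for the effectiveness rate from the final effectiveness assessment, which is not among the endpoints in Protocol 5.2.1.

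**Safety.** SAP 6.3 says "the incidence proportion of AEs will be estimated with its 95% confidence interval". No construction method is named there or in SAP 6.3.1 and 6.3.2. For subgroups, SAP 6.3.1 says that a chi-square or Fisher's exact test "will be used for comparing between subcategories of each demographics and baseline characteristics".

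**Sites.** SAP 2.2 says "A total of 3,000 patients will be enrolled at approximately 80 sites by as many as 100 or more NIS physicians". Enrolment is consecutive within site. Site does not appear in any SAP analysis or in the variable list of SAP 6.1 that feeds the optional regressions.

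**The concern.** There are two linked gaps.

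First, the SAP does not deliver what the protocol promises. In a single-arm descriptive study with no hypotheses, an interval tells the reader more than a paired-t p-value does. The protocol's own effectiveness endpoints lack one, while an endpoint found only in the SAP has one.

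Second, the named methods (paired t-test, t-test or ANOVA, chi-square or Fisher's test, exact interval) treat patients as independent. Several features of the design make some within-site correlation plausible for safety, the primary objective:

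- Patients are asked to contact their own physician about adverse events (Protocol 6.2.2.1).
- Laboratory changes are collected on medical need (Protocol 6.2.2.2 and 6.2.2.3) and become AEs only if the physician judges them clinically relevant (Protocol 5.1.2.1).
- Causality is the physician's judgment, and every AE not graded as unlikely counts as an adverse drug reaction (SAP 6.3.2).
- No investigations are required (Protocol 7.4).

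If such correlation exists, a 95% interval for overall AE incidence computed as if patients were independent will be too narrow as a statement about routine Korean practice.

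**Working it through.** **Step 1: planned output against the protocol's commitment.**

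| Endpoint (Protocol 5.2.1) | Output in SAP 6.2 and 7.3 | Interval planned? |
|---|---|---|
| HbA1c change (main) | mean, SD, paired-t p-value | no |
| HbA1c below 6.5% | frequency, percentage | no |
| HbA1c fall of at least 0.5% | frequency, percentage | no |
| FPG change | mean, SD, paired-t p-value | no |

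This part needs no arithmetic.

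**Step 2: inputs for the clustering check.** N = 3,000 and about 80 sites (SAP 2.2), so the average site size is m = 3,000/80 = 37.5. The level is two-sided 0.05 (SAP section 8). The ICC, the AE incidence, the SD of HbA1c change and the variation in site size are not in the documents and are assumed below. The plan states no interval width, and its sample size is a regulatory requirement (Protocol 7.6), so there is no precision figure to reproduce.

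**Step 3: baseline under independence.** For an assumed AE incidence of 10%, the half-width is 1.96 × √(0.1 × 0.9 / 3,000) = 1.07 percentage points. The exact interval is 8.95% to 11.13%.

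**Step 4: design effect.** DE = 1 + (m − 1) × ICC = 1 + 36.5 × ICC. Effective N = 3,000/DE. The width factor is √DE. Coverage of a nominal 95% interval is 2Φ(1.96/√DE) − 1.

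| Assumed ICC | DE | Effective N | Width factor | Half-width at 10% incidence | Coverage |
|---|---|---|---|---|---|
| 0 | 1.00 | 3,000 | 1.00 | 1.07 | 95% |
| 0.01 | 1.365 | 2,198 | 1.17 | 1.25 | 90.7% |
| 0.05 | 2.825 | 1,062 | 1.68 | 1.80 | 75.6% |
| 0.10 | 4.65 | 645 | 2.16 | 2.31 | 63.7% |

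**Step 5: uneven sites.** With an assumed coefficient of variation of site size of 0.8, DE = 1 + ((1 + 0.8²) × 37.5 − 1) × ICC = 1 + 60.5 × ICC. The width factors at ICC 0.01, 0.05 and 0.10 become 1.27, 2.01 and 2.66.

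**Step 6: HbA1c change.** With an assumed SD of 1.0, the half-width is 1.96 × 1.0/√3,000 = 0.036 points under independence, and 0.042, 0.060 and 0.077 at ICC 0.01, 0.05 and 0.10 with equal sites. The largest value over SD 0.8 to 1.5 and ICC up to 0.10 is 0.116. That is small beside the 0.5-point response threshold, so clustering matters mainly for AE proportions.

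All figures take 3,000 analysed patients. Exclusions and the absence of imputation (SAP 3.1, 3.2 and 6.4) may lower that number.

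**The case against.** The study is descriptive, tests no confirmatory hypothesis and has a regulatory sample size, so no planned decision turns on the width of an interval. The ordinary interval for HbA1c or FPG change can be rebuilt from mean, SD and n. The protocol gives common definitions of intensity and causality, which should reduce variation between sites. The optional regressions allow variables to be added, so site could enter. Sites are not described as a random sample, and treating them as one is a choice about the target population. Clustered variance also fails where events are very few, as in many of the preferred-term tables.

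Most of this limits the size of the point and does not remove it. A result that can be rebuilt is not one that is shown, which is what Protocol 7.1 promises. Permission to add a variable is not a plan to do so. The routine-practice objective makes inference beyond the participating sites reasonable, though clustered variance cannot correct non-random choice of sites. The objection about rare events stands in full and shapes the fix.

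A reader might infer three stronger things that the documents do not support:

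- That every planned interval is an exact binomial one. The exact method is named only for the effectiveness rate; the AE method is unstated.
- That the plan overstates its precision. It states no width, precision target or power, and at an ICC of 0 nothing is lost.
- That subgroup p-values are too small. Factors such as age and sex vary within sites, and for these, ignoring a positive within-site correlation can make p-values too large. The direction is not uniform.

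**Conclusion.** The mismatch on intervals is established by the texts: four protocol endpoints, including the main effectiveness endpoint, have none in the SAP. It is equally clear that no planned analysis accounts for site.

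The consequence of ignoring site is conditional. If outcomes correlate positively within site, independence-based intervals for overall AE incidence and overall means are too narrow, by a factor of 1.17 to 2.16 for assumed ICCs of 0.01 to 0.10 with equal sites, and by more with uneven ones. The coverage figures in the working follow entirely from those assumed ICCs and describe no known property of this study. No power or error-rate claim is overturned. The changes are worth making because they are cheap and meet the protocol's own commitment.

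**What to change.** 1. Add 95% confidence intervals to SAP 6.2 and 7.3 for HbA1c change, FPG change and both responder rates.
2. Name the interval method for AE incidence in SAP 6.3.
3. For overall AE incidence, mean HbA1c and FPG change and the two responder rates, report a 95% interval with site as the cluster (cluster-robust variance or GEE) and the observed ICC, beside the standard interval.
4. Keep exact intervals for rare preferred terms and for serious and unexpected events, and say in the SAP that clustered variance is not used there because it is unreliable with few events.

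This needs no new patient data. Site staff enter the data in the electronic system (Protocol 8.3), so site should be identifiable. The cost is a few lines of code, some extra table columns and, if outcomes do cluster, somewhat wider intervals than the standard ones.
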